Single-Session Extraoral Photobiomodulation Reduces Early Postoperative Pain but Not Edema or Trismus After Impacted Mandibular Third Molar Extraction: A Randomized Controlled Trial

ClinicalTrials.gov Identifier: NCT07522918

Date of Document: January 30, 2025

Necmettin Erbakan University, Faculty of Dentistry, Department of Oral and Maxillofacial Surgery

1. Study Design and Ethical Approval

This prospective, parallel-group randomized controlled clinical trial was conducted at Necmettin Erbakan University. The study protocol was approved by the Institutional Ethics Committee for Non-Drug and Non-Medical Device Research (Decision No: 2025/535). Written informed consent was obtained from all participants prior to enrollment.

2. Patient Selection

A total of 70 patients (age range: 17–25 years) with asymptomatic mesioangular impacted mandibular third molars (Pell–Gregory Class IB) were enrolled. Participants were randomized into a PBM group (n=35) or a control group (n=35) using a computer-generated random sequence.

Inclusion Criteria:

- Indication for extraction of an impacted mandibular third molar.
- ASA I status (absence of systemic disease).
- Healthy status of the impacted tooth and surrounding tissues.

Exclusion Criteria:

- Pregnancy or lactation.
- Regular use of NSAIDs or antibiotics within the preceding week.
- Active smoking.

3. Surgical Procedure

All surgical procedures were performed by a single surgeon following a standardized protocol. Local anesthesia was achieved using 4% articaine hydrochloride with 1:100,000 epinephrine. A full-thickness mucoperiosteal flap was raised, followed by standardized bone removal and tooth sectioning under saline irrigation. Wound closure was performed with 3-0 silk sutures. All patients received a standardized postoperative medication regimen including amoxicillin/clavulanic acid, benzydamine HCl/chlorhexidine gluconate mouth rinse, and dexametopfen.

4. Photobiomodulation (PBM) Protocol

The PBM group received a single session of extraoral therapy immediately following surgery using a dual-wavelength GaAlAs laser (650 nm + 904 nm, GRR Laser).

- **Application Time:** 10 minutes.
- **Total Energy:** 270 J (27 J/min).
- **Power Density:** 4.54 mW/cm².
- **Energy Density:** 2.73 J/cm². The probe was positioned in stationary contact over the mandibular angle–ramus region. The control group received no laser application.

5. Outcome Variables

- **Pain:** Evaluated using a 100-mm visual analog scale (VAS) at postoperative days 2 and 7.
- **Edema:** Measured via facial distance measurements between anatomical landmarks (tragus–labial commissure, gonion–lateral canthus, gonion–labial commissure) at baseline, day 2, and day 7.
- **Trismus:** Assessed by measuring maximum interincisal distance (MID) using a sliding caliper at baseline, day 2, and day 7.
- **Quality of Life:** Evaluated using a 100-mm OHRQoL VAS scale (0 = worst, 100 = normal) at postoperative days 2 and 7.

6. Statistical Analysis

Normality was assessed using Shapiro-Wilk and Kolmogorov–Smirnov tests. Between-group comparisons were performed using Independent Samples t-tests or Mann–Whitney U tests. Repeated measures ANOVA with Bonferroni correction was used for longitudinal data. Significance was set at $p < 0.05$.

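### The title states that the laser does not reduce edema or trismus, but the plan has only difference tests with no margin or interval, so non-significance alone cannot establish this

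*Combined protocol and SAP*

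**What the plan says.** The title is worded as a result: treatment "Reduces Early Postoperative Pain but Not Edema or Trismus". Section 2 gives the size and allocation: "Participants were randomized into a PBM group (n=35) or a control group (n=35) using a computer-generated random sequence".

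Section 5 defines edema by three facial distances and trismus by maximum interincisal distance (MID). All four are measured at baseline, day 2 and day 7.

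Section 6 is the whole analysis plan. After normality checks, "Between-group comparisons were performed using Independent Samples t-tests or Mann–Whitney U tests", and "Repeated measures ANOVA with Bonferroni correction was used for longitudinal data". The significance level is 0.05, with sidedness not stated. The document gives no confidence interval, equivalence or non-inferiority margin, smallest worthwhile difference, SD, power statement or sample-size rationale. It reports no estimate or p-value for edema or trismus.

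**The concern.** Every procedure in Section 6 asks whether the groups differ. Such a procedure can support a claim that they do. When it fails to reject, it leaves open both a zero effect and any effect the trial was too imprecise to see. An interval set against a margin can separate these, and the plan specifies neither. Under the stated rule, the only evident route to 'Not' in the title is p ≥ 0.05.

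Edema and trismus are two of the four outcomes, and the title is the most visible statement of the trial. A clinician or evidence synthesiser could record a negative efficacy finding that the stated analysis does not establish.

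**Working it through.** The document has no power or precision figure to reproduce, and no SD, so everything below is in SD units.

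**Inputs.** n = 35 per arm (Section 2), all assumed analysed. Alpha = 0.05 (Section 6), two-sided assumed. Correlation r between baseline and postoperative values: not given; 0.5 and 0.7 assumed.

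**Standard error of a difference in means.** √(2/35) = 0.2390 SD.

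**95% interval half-width.**
- Unadjusted: t(0.975, 68 df) × 0.2390 = 1.9955 × 0.2390 = 0.477 SD.
- Baseline-adjusted: t(0.975, 67 df) × 0.2390 × √(1 − r²). At r = 0.5 this is 1.9960 × 0.2390 × 0.866 = 0.413 SD. At r = 0.7 it is 1.9960 × 0.2390 × 0.714 = 0.341 SD.

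**What a non-significant unadjusted result leaves open.** If the observed difference is exactly zero, benefits up to 0.48 SD lie inside the interval. If it favours the laser and only just misses significance (0.477 SD), the interval reaches 2 × 0.477 = 0.95 SD.

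**Power of one unadjusted two-sided test** (noncentral t, 68 df, noncentrality d × √(35/2) = 4.183 d):

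| True benefit d | Noncentrality | Power | Chance of missing it |
|---|---|---|---|
| 0.3 SD | 1.255 | 23.6% | 76.4% |
| 0.5 SD | 2.092 | 54.1% | 45.9% |
| 0.68 SD | 2.845 | 80.1% | 19.9% |

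With the Mann–Whitney test (relative efficiency 0.955), power at 0.5 SD is about 53%.

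**Difference detectable with 80% power.** Normal approximation: (1.960 + 0.842) × 0.2390 = 0.67 SD; noncentral t gives 0.68 SD. If the test were one-sided it would be 0.59 SD. With baseline adjustment, 0.67 × √(1 − r²) is 0.58 SD at r = 0.5 and 0.48 SD at r = 0.7.

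**Power to exclude a benefit of size m when the true difference is zero** (unadjusted, one-sided 0.025, normal approximation): Φ(m/0.2390 − 1.960).
- m = 0.3 SD: Φ(−0.705) = 24%
- m = 0.5 SD: Φ(0.132) = 55%
- m = 0.67 SD: Φ(0.843) = 80%
- m = 0.8 SD: Φ(1.387) = 92%

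**The case against.** Several points on the other side stand.

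**Sample size.** A reader might infer that 35 per arm can never support a no-benefit claim. The documents do not show that, because it depends on an SD and a margin they do not give. For a margin near 0.68 SD the trial has about 80% power to exclude a benefit when there is none, and more for wider margins. The gap lies in the missing margin and interval rather than in the sample size alone.

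**Results.** A reader might also take it as established that the edema and trismus tests were non-significant. No result is shown. An estimate near zero or favouring control could exclude a worthwhile benefit and justify the wording.

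**Precision.** The 0.48 SD half-width is the unadjusted figure. Section 5 collects baseline values for these outcomes, so a tighter interval is available, although Section 6 does not mention adjustment.

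**Single-test power.** The miss rates apply to one comparison. They do not give the chance that every edema and trismus comparison misses, which depends on correlations and a pattern of effects that are not stated.

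**The contrast with pain.** A reader might see a claim that the effect on pain exceeds the effect on edema. The title reports separate outcomes on different scales and makes no such comparison.

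Finally, this form of title is common shorthand. That may explain it, but it supplies no evidence for the negative half.

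**Conclusion.** The concern holds as a fault of inference. The title asserts absence of effect on two outcomes, while the plan supplies only difference tests, with nothing that could turn non-significance into evidence of no worthwhile benefit. That the title rests on non-significance is inferred from the title and Section 6 together.

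Benefits somewhat below about 0.68 SD could readily be missed in a single unadjusted test. Whether they remain open in this trial cannot be settled from the document, because neither the observed interval nor a margin is given. These figures assume 35 analysed per arm and two-sided testing; the adjusted ones also assume the stated correlations. This should be fixed, but it concerns wording and reporting and does not call the randomisation, measurements or tests into question.

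**What to change.** 1. Replace the negative half of the title with wording such as *no significant difference in edema or trismus was detected*, provided the results bear that out.
2. In Section 6, specify for each of the three facial distances and for MID, at days 2 and 7, the between-group difference from an ANCOVA on the baseline value already collected, with its 95% confidence interval in mm. That is 4 measures × 2 days = 8 intervals.
3. Keep a statement that the laser does not reduce edema or trismus only if the whole interval excludes a smallest worthwhile benefit in mm, justified without reference to the trial data.

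The cost is a title change, a short addition to Section 6 and a column of intervals. No new data are needed. The downside is a less definite stated conclusion.

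### Controls get no laser and no sham or masking is described, so the self-rated pain benefit in the title cannot be attributed to the laser rather than to expectation

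*Combined protocol and SAP*

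**What the plan says.** Section 1 describes the design: "This prospective, parallel-group randomized controlled clinical trial was conducted at Necmettin Erbakan University". It uses no blinding term. Section 2 reports the allocation: "Participants were randomized into a PBM group (n=35) or a control group (n=35) using a computer-generated random sequence".

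Section 3 describes only local anesthesia ("Local anesthesia was achieved using 4% articaine hydrochloride with 1:100,000 epinephrine"), with no mention of sedation. Section 4 defines the two conditions. In the active arm, "The PBM group received a single session of extraoral therapy immediately following surgery", for 10 minutes, and "The probe was positioned in stationary contact over the mandibular angle–ramus region". For the other arm the whole description is "The control group received no laser application".

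In section 5, pain is "Evaluated using a 100-mm visual analog scale (VAS) at postoperative days 2 and 7". Quality of life is a second 100-mm VAS on the same days. Edema and trismus are physical measurements: facial distances, and mouth opening by caliper. Section 6 lists t-tests or Mann–Whitney tests between groups and repeated measures ANOVA over time, at the 0.05 level.

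The title claims a reduction in early postoperative pain and none in edema or trismus. It does not mention quality of life. The text does not mention a sham, an inactive probe, concealment of the sequence, or masking of patient, operator, measurer or analyst.

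**The concern.** An awake patient either has a probe held against the jaw for 10 minutes or, as the control condition is written, has nothing. Two of the four outcomes are then rated by that patient. Knowledge of treatment, and the extra attention that comes with a session, can shift such ratings without any action of the light on tissue.

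Randomization balances the arms at baseline. It does not protect against differences in reporting that arise after allocation becomes known. What is at stake is the one positive claim in the title, which is worded as an effect of photobiomodulation and rests on a self-rated scale.

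**Working it through.** **Can patients be expected to know their arm?** Set sections 3 and 4 side by side: local anesthesia only, a perceptible 10-minute contact procedure in one arm, and no procedure described in the other. That patients know their arm is an inference, but a strong one.

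**Can the planned analysis separate the two explanations?** Every test in section 6 compares observed scores between arms or over time. If the laser shifts mean pain by d and expectation shifts it by b, the between-arm difference estimates d + b. Nothing in the plan identifies b.

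**How large could the effect on the test be?** The plan gives no SD, target difference or power figure, so there is nothing of its own to reproduce. The following is an illustration.

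- From the document: 35 per arm; significance level 0.05 (sidedness not stated, two-sided taken here); t-test at a single time point.
- Assumed: VAS SD of 15 to 30 mm; true laser effect d = 0; pure expectation shift b of 5 or 10 mm in favor of PBM.

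Standard error: SE = SD × √(2/35) = 0.239 × SD.

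Smallest observed difference reaching p<0.05: t(0.975; 68 df) × SE = 0.477 × SD.

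Rejection rate: noncentral t with 68 df and noncentrality b/SE, both tails.

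| Assumed SD (mm) | SE (mm) | Smallest significant difference (mm) | p<0.05 if b = 5 mm | p<0.05 if b = 10 mm |
|---|---|---|---|---|
| 15 | 3.59 | 7.2 | 28.0% | 78.5% |
| 20 | 4.78 | 9.5 | 17.8% | 54.1% |
| 25 | 5.98 | 11.9 | 13.1% | 37.8% |
| 30 | 7.17 | 14.3 | 10.6% | 28.0% |

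With b = 0 the rate is 5%, of which 2.5% favors PBM. With b > 0 almost all rejections favor PBM; at SD 30 mm and b = 5 mm, for example, 10.2 of the 10.6 percentage points do. The last cell equals the first because 10/30 and 5/15 are the same standardized shift.

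**Cost of a sham:** 35 controls × 10 minutes = 350 minutes, or 5.8 hours.

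**The case against.** **The document is short and silent, and silence is not a statement.** It never calls the trial open-label, and withholding laser does not logically exclude an inactive probe. This stands as a limit on wording: one can say that no sham or masking is described, not that none was used. It does not remove the point, because the control condition as written is an untreated one, and a sham that was used would still have to be described.

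**A reader might infer that the title's pattern shows bias.** The documents do not support that. A real analgesic effect would also lower pain without changing swelling or mouth opening. Mouth opening depends partly on patient effort, so expectation might have been thought to reach it too, yet the title reports no benefit there. Quality of life is also self-rated, and no result for it is given. Compatibility with both explanations is the most that can be said.

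**A reader might infer that the surgeon and the measurer knew the allocation.** The text does not say so. "All surgical procedures were performed by a single surgeon following a standardized protocol" concerns standardization, not knowledge of the arm. No measurer is named, and the time at which allocation was opened is not given. These are gaps in reporting.

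**The illustration rests on assumptions.** Both the SD and the shift are assumed, and the resulting range is wide. This stands: the figures show that a shift could matter, not that one occurred.

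**No treatment is a legitimate comparator.** This also stands. Because patients were randomized, a difference can be causal for the session as a whole, meaning light plus contact plus attention. What the design cannot supply is attribution to the laser itself.

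**Conclusion.** The concern holds in a limited form. With an untreated control, no described sham or masking, and self-rated pain and quality of life, the plan cannot distinguish a laser effect from expectation, and the title's pain claim is worded as if it could. This conclusion depends on none of the assumed figures. It rests on the plain reading of section 4 and on the inference that a patient under local anesthesia notices a 10-minute contact session.

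As to size, under an assumed SD of 15–30 mm and no laser effect, significance would occur in 11–28% of trials with a 5 mm expectation shift and in 28–79% with a 10 mm shift, against a nominal 5%. The true shift is unknown and could be zero.

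Neither a finding that the result is biased nor a finding that the surgeon or measurer was unmasked follows from the documents.

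**What to change.** The text is in the past tense and the title states a result, so the conclusion comes first.

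1. **If enrolment is finished.** If no sham was used, state that patients were not masked, and limit the pain and quality-of-life conclusions to *PBM session compared with no treatment, without patient masking*, with no claim of a laser-specific effect. Reword the title to match. Keep the randomized comparison: wording such as *associated with* would discard it without reason. If a sham was used, describe it. Either way, report when allocation was opened and whether the surgeon and whoever took the measurements knew it. This costs only rewording.

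2. **If any patients remain to be enrolled.** Give controls the same 10-minute probe placement with emission off, if the device allows it. Cover the eyes in both arms, because the 650 nm component is visible. Report separately the patients enrolled before the change. Open each allocation only after wound closure, and withhold it from whoever takes the measurements. The cost is about 10 minutes of chair time per control, at most 5.8 hours in total, with no extra visit.

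### Edema is three facial distances at two postoperative visits with no combined measure, key visit, decision rule or planned baseline adjustment, so the single verdict on edema rests on no defined result.

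*Combined protocol and SAP*

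**What the plan says.** Combined protocol and SAP, section 5 (Outcome Variables), describes edema as "Measured via facial distance measurements between anatomical landmarks". It lists the distances and times as "tragus–labial commissure, gonion–lateral canthus, gonion–labial commissure) at baseline, day 2, and day 7". No sum, mean, percentage change, key distance or key visit follows.

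Section 6 (Statistical Analysis) treats all outcomes together. For arm comparisons it says "Between-group comparisons were performed using Independent Samples t-tests or Mann–Whitney U tests". It adds "Repeated measures ANOVA with Bonferroni correction was used for longitudinal data". The significance level is 0.05. The section does not say which method applies to edema, how the three distances are handled, whether raw values or changes from baseline are tested, or which comparisons Bonferroni covers.

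The title gives a single conclusion: "Reduces Early Postoperative Pain but Not Edema or Trismus".

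**The concern.** Edema is one construct, but the plan yields several results for it: three if each distance has one longitudinal test, six if each distance is compared at day 2 and at day 7. Nothing says how these become one yes or no. Three rules are compatible with the text: any distance significant, all distances significant, or one distance chosen as decisive. They have very different error rates and power, so a reader cannot tell how strong the negative statement in the title is.

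The baseline distances are a second loose end. They are collected, but a t-test or Mann–Whitney U test on day 2 or day 7 values ignores them, and differences in face size between people then stay in the error term. The plan does not say that changes from baseline are tested instead.

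**Working it through.** The documents give no sample-size calculation, SD, correlation or target effect for edema, so there is no planned figure to reproduce. The check asks how much the missing rule matters.

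**Inputs from the documents:** 35 per arm (section 2); level 0.05 (section 6); three distances and two postoperative visits (section 5).

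**Assumptions:** two-sided tests; equal SDs; a standardized effect d = 0.5 on each distance; pairwise correlation ρ between distances of 0.3 to 0.7, with 0.9 as an extreme; correlation 0.6 between day 2 and day 7. No baseline adjustment is included.

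**Step 1, one distance.** The noncentrality is d × √(n/2) = 0.5 × √17.5 = 2.09 on 68 degrees of freedom. Power is 54%.

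**Step 2, mean of three.** Its SD relative to one distance is f = √((1 + 2ρ)/3). The standardized effect becomes 0.5/f, with the same power formula. For ρ = 0.3, f = √(1.6/3) = 0.73, the effect is 0.68 and power is 81%.

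**Step 3, effect on one distance only.** The mean then shifts by 0.5/3 = 0.167, so the standardized effect is 0.167/f.

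**Step 4, the other rules.** These were simulated with t-tests, 40,000 trials per setting (20,000 for the six-test rate).

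| | ρ 0.3 | ρ 0.5 | ρ 0.7 | ρ 0.9 |
|---|---|---|---|---|
| f | 0.73 | 0.82 | 0.89 | 0.97 |
| Power, mean of three | 81% | 71% | 64% | 57% |
| Power, any of three, Bonferroni | 67% | 62% | 55% | 47% |
| Power, any of three, unadjusted | 84% | 79% | 73% | 65% |
| Power, all three significant | 23% | 28% | 35% | 43% |
| False positives, any of three, unadjusted | 14% | 13% | 11% | 9% |
| False positives, any of six, unadjusted | 23% | 21% | 18% | 14% |
| Effect on one distance only: power, mean | 16% | 13% | 12% | 11% |
| Effect on one distance only: power, any of three, Bonferroni | 38% | 38% | 38% | 38% |

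A normal approximation in place of the t distribution moves the power figures up by about one or two points; Bonferroni any-of-three becomes 57–68% for ρ from 0.7 to 0.3.

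**Step 5, unequal SDs.** Take SDs of 1, 1 and 2, ρ = 0.5 and a common shift of 0.5. The variance of the sum is 1 + 1 + 4 + 2 × (0.5 + 1 + 1) = 11, so the SD of the mean is √11/3 = 1.11. The standardized effect is 0.5/1.11 = 0.45 and power is 46%, below the 54% for one of the less variable distances.

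**Step 6, baseline.** If a distance correlates r with its own baseline (not given), ANCOVA leaves about 1 − r² of the variance of the follow-up value: 0.75 at r = 0.5 and 0.36 at r = 0.8. A change score leaves 2(1 − r), which is never smaller, because 1 − r² = (1 − r)(1 + r) and 1 + r is at most 2.

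**The case against.** Several stronger readings are tempting, and the documents do not support them.

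- **That six unadjusted tests were planned.** The plan never says the distances are tested separately at each visit. Edema is longitudinal, and repeated measures ANOVA could give one group-by-time result per distance. Bonferroni is mentioned, so adjustment cannot be assumed absent; its scope is simply not stated. ANOVA could also take baseline in as a time point, though the plan does not say so. This objection stands: the defect is that the rule is unspecified.
- **That having no composite always loses power.** Unadjusted any-of-three testing has more power than the mean (73–84% against 64–81%) and pays for it in false positives. If the effect sits on one distance, the mean does much worse than Bonferroni any-of-three. At ρ = 0.9 the gain over one distance is about 3 points, and with unequal SDs an unweighted mean can do worse than a less variable distance. This stands too.
- **That the Bonferroni comparator is one named distance at 0.05/3, with 36% power.** Whoever adjusts for three tests looks at all three, so the fair figure is 55–67%.
- **That false-positive inflation undermines the title.** The stated edema result is negative, so inflation bears less on that claim than on how a positive result would have been read. Nor do the documents show that a real edema effect was missed.

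The gap itself is untouched. Even with ANOVA for each distance there are three results and no rule for combining them. Choosing the mean over a sum, percentage change or key distance is a judgement; naming one measure is not optional if one verdict is to be given.

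**Conclusion.** The point holds as a gap in specification, and it should be fixed because it sits under a headline conclusion. The absence of a combined measure, key visit and decision rule follows from the text alone and needs no assumption. Its size does need assumptions. For ρ from 0.3 to 0.7, a shared 0.5 SD effect would be found with power anywhere from 23% (all three required) to 84% (any of three, unadjusted), depending on a rule that the plan leaves open. False positives under the unadjusted any rule are 11–14% over three tests, or about 18–23% over six.

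The mean of three gains about 10 to 27 points over one distance (64 − 54 and 81 − 54) and about 9 to 14 points over Bonferroni any-of-three (64 − 55 and 81 − 67). These gains depend on a shared effect, roughly equal SDs and moderate correlation. None of those can be checked from the documents, so the power gain supports the fix but is not an established loss in this trial.

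**What to change.** In section 5, define one edema score: the mean of the three distances, in mm, at each visit. In section 6, compare arms on that score at day 2 (main) and day 7 by ANCOVA with the baseline score as covariate, and report the adjusted difference with its 95% CI. State that the day 2 comparison decides the edema conclusion, and what the Bonferroni correction covers. Report each distance with its own baseline-adjusted estimate and CI as supportive. Base the verdict on the interval, which shows which edema effects the trial can and cannot exclude.

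No new data are needed. The real cost is dilution: an effect confined to one distance has only 12–16% power on the mean (ρ 0.7 to 0.3), against about 38% for Bonferroni any-of-three. The supportive estimates would display such an effect but not restore that power. If the SDs of the distances differ widely, say so and justify the equal weighting. The title already states a result, so if the score is adopted after the results are known, label it post hoc.

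### Section 6 gives no rule for choosing between the t-test and Mann–Whitney, so the test and the effect measure can depend on the data and can differ between day 2 and day 7

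*Combined protocol and SAP*

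**What the plan says.** The whole analysis plan is in Section 6 (Statistical Analysis), in four sentences. The first is "Normality was assessed using Shapiro-Wilk and Kolmogorov–Smirnov tests". The second is "Between-group comparisons were performed using Independent Samples t-tests or Mann–Whitney U tests". The third is "Repeated measures ANOVA with Bonferroni correction was used for longitudinal data". The last sets the significance level at 0.05 without stating sidedness.

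Section 6 does not state:
- that the normality result selects the test (the order of the sentences implies it);
- which of the two normality tests governs, or what is done if they disagree;
- what is tested for normality: each arm, pooled data, residuals or changes;
- whether Kolmogorov–Smirnov is corrected for estimated parameters (the Lilliefors form);
- whether the choice is made once, per outcome or per visit;
- which effect measure is reported.

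No other section fills these gaps. Section 2 gives 35 patients per arm. Section 5 lists the outcomes. Pain is "Evaluated using a 100-mm visual analog scale (VAS) at postoperative days 2 and 7", and quality of life uses a similar bounded scale at the same two visits, so neither has a baseline. Edema (three facial distances) and maximum interincisal distance (MID) are measured at baseline, day 2 and day 7.

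**The concern.** A t-test addresses a difference in means. Mann–Whitney is a rank comparison and addresses the probability that a patient in one arm scores higher than a patient in the other. If normality results decide which is used, the data decide both the test and the quantity being compared. Two pretests of different sensitivity with no tie-break leave that decision open whenever they conflict.

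Bounded scores are where this matters most. Pain may be roughly symmetric at day 2 and crowded near zero at day 7, so one outcome could be reported as a mean difference at one visit and a rank result at the next. The two could not be compared directly. The document's title contrasts early pain with other results, so a common scale across visits has practical value.

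**Working it through.** The plan states no figure to reproduce: there is no power calculation, SD or effect size. The check is therefore by simulation, with the assumptions stated.

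**Inputs from the document:** 35 per arm (Section 2), alpha 0.05 (Section 6), and the outcomes and visits in Section 5.

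**Assumed:** two-sided testing, no dropout, the distributions below, Lilliefors-corrected Kolmogorov–Smirnov (simulated 5% critical value 0.148 at n = 35), normality tested in each arm, and Mann–Whitney used if either arm rejects.

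**1. How often the two pretests conflict.** Four shapes (normal; 100×Beta(2,3), Beta(1.5,3) and Beta(0.8,5)), 8,000 trials each: 4–31% of two-arm comparisons. A wider set of nine shapes, 6,000 trials each, gave the results below. VAS parameters are before clipping to 0–100. The fourth column takes the more favourable result when the pretests conflict.

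| Shape | Conflict % | Type I, t alone % | Type I, favourable on conflict % | Difference (points) |
|---|---|---|---|---|
| Normal | 11.5 | 5.3 | 5.6 | +0.3 |
| VAS mean 40, SD 20 | 9.6 | 4.5 | 4.6 | +0.1 |
| VAS mean 25, SD 20 | 43.2 | 5.4 | 5.9 | +0.5 |
| VAS mean 10, SD 15 | 10.1 | 5.4 | 5.1 | −0.3 |
| Beta(2,3) | 18.3 | 5.1 | 5.4 | +0.3 |
| Beta(1.5,4) | 34.3 | 4.9 | 5.5 | +0.6 |
| Beta(1,6) | 9.0 | 4.8 | 5.1 | +0.3 |
| Lognormal, log-SD 0.4 | 27.2 | 4.8 | 5.7 | +0.9 |
| Gamma, shape 4 | 31.9 | 4.6 | 5.6 | +1.0 |

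The Monte Carlo SE of each error rate is √(0.05×0.95/6000) ≈ 0.28 points. Conflict peaks at intermediate skew. With near-normal data both pretests usually accept, and with strong skew both usually reject.

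**2. Over the whole plan.** Post-operative comparisons: edema 3×2 = 6, MID 2, pain 2, quality of life 2, total 12. At the normal-data rate, the chance of at least one conflict is 1 − (1 − 0.115)^12 ≈ 0.77. This treats the 12 as independent, which they are not, so it is illustrative only.

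**3. Different tests at day 2 and day 7.** Shapiro–Wilk gate alone, applied per visit, assumed correlation 0.5:

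| Day 2 → day 7 (no effect) | Mann–Whitney at day 2 | Mann–Whitney at day 7 | Tests differ |
|---|---|---|---|
| Normal at both visits | 10.4% | 10.7% | 18.7% |
| VAS mean 40 → 25 | 8.0% | 58.1% | 56.4% |
| VAS mean 40 → 10 | 8.0% | about 100% | 92.0% |

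With a 0.5 SD effect the last column becomes 18.4%, 78.8% and 83.6%.

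**4. Whether the choice of test matters.** In the day-2 scenarios of step 3, the t-test and Mann–Whitney gave different verdicts at 0.05 in 1.4–2% of null trials and 6–7% of trials with a 0.5 SD effect. Over the four shapes of step 1, with an effect of about 0.5 SD, the range was 7–19%.

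**5. Type I error on the four shapes.** Taking the smaller p only on conflict gave 4.8–5.5%, against 4.5–5.1% for the t-test alone (8,000 trials per shape). With 20,000 trials per shape (SE about 0.15 points) it was 5.2–5.6% against 4.9–5.1%, an excess of about 0.2–0.6 points.

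**The case against.** The strongest reply is that little is at stake. Both tests hold their level at this sample size, and exploiting the gap adds only a fraction of a point to type I error. That stands. A reader might infer real inflation from the fact that always taking the smaller of the two p-values gives 5.1–7.0% in simulation. That procedure ignores any normality gate, so it is not a reading of Section 6.

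Three other strong readings go beyond the document:
- That the pretests are stated to select the test. This is implied only. If no link was intended, however, Section 6 has no selection rule at all.
- That the repeated measures ANOVA is run whatever the pretests show. Section 6 names no alternative to it, but does not say this.
- That the test was in fact picked after seeing the results. The text leaves that open and shows nothing either way.

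It is also fair to say that Mann–Whitney can be reported in mm, through the Hodges–Lehmann estimate and its CI under a shift assumption, and that a plain t-test does not adjust for baseline either. Both are right. But Section 6 names no effect estimate, and a location shift is still not a mean difference unless a pure shift holds. Nor can the pretest be called worthless on this evidence, because the power of the alternatives was not compared.

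**Conclusion.** The point holds as a gap in specification that should be closed, with a modest effect. Neither the between-group test nor the effect scale is fixed for any outcome or visit. Conflict between the pretests is plausible: about 4–31% of comparisons on the four shapes, and 9–43% on the wider set. A change of test between visits is possible even with normal data, and likely if pain falls toward the floor by day 7. The choice can decide a marginal result.

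No material error inflation should be claimed. The excess is about half a point on the four shapes and about one point at most in any shape tried; the largest values came from the two unbounded skewed shapes. All rates depend on the assumed distributions, the Lilliefors correction and the rule that either arm rejecting triggers Mann–Whitney. The document gives none of these.

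**What to change.** Remove the normality gate and fix one analysis per outcome, used at both day 2 and day 7:
- **Pain and quality of life** (no baseline): Welch t-test.
- **Each edema distance and MID:** linear model for the post-operative value with treatment arm and that patient's baseline measurement.
- **Reporting:** for every comparison, the between-group difference in mm with a 95% CI.
- **Sensitivity:** Mann–Whitney with the Hodges–Lehmann shift for every outcome and visit, labelled as such. There should be no switch triggered by skewness, since that would bring the same problem back.

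The cost is a rewrite of Section 6 and a re-analysis of data already collected; no new patients or measurements are needed. Some power may be lost against a rank test if day-7 scores are strongly skewed and the effect is a pure shift. The sensitivity analysis would show this.

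Rewording cannot restore pre-specification. The document is written in the past tense and its title states results, so the report must say that the single analysis was fixed after the data were seen. It should show both sets of results.
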